Name of finished product: Not applicable			
Name of active ingredient: BI 425809			
Protocol date: 29 June 2018	Trial number: 1346-0016		Revision date: 25Sep2018
Criteria for pharmacokinetics:	
Primary endpoints: Mass balance recoveries of total radioactivity in urine and faeces: Amount of radioactivity excreted as a percentage of the administered dose (fe_{0-t2}) for urine and faeces
 
Secondary endpoints: Assessment of the oral pharmacokinetics of a solution formulation of BI 425809 XX (C-14) by calculation of the following parameters for total radioactivity and BI 425809 in plasma: C_{max} and AUC_{0-tz}
		
Criteria for safety:	Adverse events (AEs) including clinically relevant findings from the physical examination, safety laboratory tests, 12-lead electrocardiogram (ECG), vital signs (blood pressure [BP], pulse rate [PR])		
Statistical methods:	Descriptive statistics and graphical displays.		

FLOW CHART

Visit	Day	Planned time (relative to 1st drug administration [h:min])	Approximate clock time of actual day [h:min]	Event and comment	Safety laboratory	PK _{blood/plasma} ²	PK _{urine} ⁶	PK _{faeces} ⁷	12-lead ECG	Vital signs (BP, PR)	Questioning for AEs and concomitant therapy ⁹
1	-21 to -2			Screening (SCR) ¹	x				x	x	
2	-1	-18:00	14:00	Admission to trial site	x ⁵						x
		-14:00	18:00	Dinner							
		-10:30	21:30	Snack (voluntary) ¹⁵							
	1	-2:00	06:00		x ³	x ³	x ³	x ¹⁴	x ³	x ³	x ³
		0:00	08:00	Drug administration			+	+			
		0:30	08:30			x					
		0:45	08:45			x					
		1:00	09:00			x					
		1:30	09:30			x					
		2:00	10:00	240 mL fluid intake		x					
		4:00	12:00	240 mL fluid intake, thereafter lunch ⁴	x ⁸	x	+		x	x	x
		6:00	14:00			x					
		8:00	16:00	Snack (voluntary) ⁴		x	+				
		11:00	19:00	Dinner							
		12:00	20:00			x	+		x	x	x
		13:30	21:30	Snack (voluntary)							
	2	24:00	08:00			x	+	+		x	x
		36:00	20:00			x					
	3	48:00	08:00		x ⁸	x	+	+			x
	4	72:00	08:00			x	+	+			x
	5	96:00	08:00			x	+	+			x
	6	120:00	08:00			x	+	+			x
	7	144:00	08:00			x	+	+			x
	8	168:00	08:00		x ⁸	x	+	+			x
	9	192:00	08:00			x	+	+			x
	10	216:00	08:00			x	+	+			x
	11	240:00	08:00			x	+	+			x
	12	264:00	08:00			x	+	+			x
	13	288:00	08:00			x	+	+			x
	14	312:00	08:00			x	+	+			x
	15	336:00	08:00	Discharge from trial centre	x	x	+	+	x	x	x
	20	461:00	13:00	Start home collection				+			
	21	485:00	13:00	Admission to trial site ^{11,12}		x	+	+			x
	22	509:00	13:00	Discharge from trial site ¹¹			+	+			x

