	27	629:00	13:00	Start home collection				+			
	28	653:00	13:00	Admission to trial site ^{11,12}		x	+	+			x
	29	677:00	13:00	Discharge from trial site ¹¹			+	+			x
	34	797:00	13:00	Start home collection				+			
	35	821:00	13:00	Admission to trial site ^{11,12}	x	x	+	+			x
	36	845:00	13:00	Discharge from trial site ¹¹			+	+			x

Visit	Day	Planned time (relative to 1 st drug administration [h:min])	Approximate clock time of actual day [h:min]	Event and comment	Safety laboratory	PK ² _{blood/plasma}	PK ⁶ _{urine}	PK ⁷ _{faeces}	12-lead ECG	Vital signs (BP, PR)	Questioning for AEs and concomitant therapy ⁹
2	41	965:00	13:00	Start home collection							
	42	989:00	13:00	Admission to trial site ^{11,12}		x	I	I			x
	43	1013:00	13:00	Discharge from trial site ¹¹			I	I			x
	48	1133:00	13:00	Start home collection				I			
	49	1157:00	13:00	Admission to trial site ^{11,12}		x	I	I			x
	50	1181:00	13:00	Discharge from trial site ¹¹			I	I			x
3	15-50			End of trial (EOT) examination ^{10,13}	x				x	x	x

- Subject must be informed and written informed consent obtained prior to starting any screening procedures. Screening procedures include physical examination, check of vital signs, ECG, safety laboratory (including drug screening), demographics (including determination of body height and weight, smoking status and alcohol history), relevant medical history, concomitant therapy and review of inclusion/exclusion criteria.
- Pharmacokinetics (PK): BI 425809 and metabolites in plasma; [¹⁴C]-radioactivity in whole blood and plasma (see [Section 5.5.2.1](#)). Blood sampling for an individual subject can be stopped if [¹⁴C]-radioactivity in plasma is below limit of detection (< LLOQ 10 dpm/mL) at two consecutive sampling time points for this subject (earliest stop on day 15).
- The time is approximate; the procedure is to be performed and completed within 2 h prior to drug administration.
- If several actions are indicated at the same time point, the intake of meals will be the last action.
- Safety lab including urine drug screening and alcohol test.

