- Urine collection intervals (for PK/[¹⁴C]-radioactivity assessment and metabolic profiling; planned time): on Day -1 or Day 1 predose (blank) sample within 2 h before drug administration, on Day 1 prior to start of urine collection voiding of the bladder, 0-4, 4-8, 8-12, 12-24; 24-48, 48-72, 72-96, 96-120, 120-144, 144-168, 168-192, 192-216, 216-240, 240-264, 264-288, 288-312 and 312-336 hours after drug administration. Thereafter, if warranted, 24 h collections are to be performed every 7 days starting on day 21. When the release criteria for radioactivity recovery have been met then urine sampling for PK will be stopped (earliest stop on day 15).
- All stools (for PK and metabolic profiling) will be collected quantitatively in portions up to 336 hours (sampling intervals of 0-24, 24-48, 48-72, 72-96, 96-120, 120-144, 144-168, 168-192, 192-216, 216-240, 240-264, 264-288, 288-312 and 312-336 hours) after drug administration. Thereafter, if warranted, 24 h collections are to be performed every 7 days starting on day 20. A blank sample will be collected before drug administration on Day -1 or Day 1. Collection of the predose faeces sample will start from approximately -48 h before admission (see [Section 5.5.2.3](#)). When the release criteria for radioactivity recovery have been met then faeces sampling for PK will be stopped (earliest stop on day 15).
- Only measurement of haematocrit
- AEs and concomitant therapies will be recorded throughout the trial, but will be specifically asked for at the time points indicated in the [Flow Chart](#) above.
- End-of-trial (EOT) examination to be performed within 1 to 7 days after last discharge from the study centre, or, if all once-weekly 24 h sampling periods are needed, prior to discharge on Day 50. End of trial examination includes physical examination, vital signs, ECG, safety laboratory, recording of AEs and concomitant therapies.
- The planned times for admission, discharge, start and end of the urine and faeces collection intervals are approximate. The procedures are to be performed within a time window of +/- 4 h to the planned time.

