In accordance with the European Medicines Agency initiative on Important Medical Events, Boehringer Ingelheim has set up a list of further AEs, which by their nature, can always be considered to be ‘serious’ even though they may not have met the criteria of an SAE as defined above.

The latest list of ‘Always Serious AEs’ can be found in the EDC system, an electronic data capture system which allows the entry of trial data at the trial site. These events should always be reported as SAEs as described above.

Adverse events of special interest

The term adverse events of special interest (AESI) relates to any specific AE that has been identified at the project level as being of particular concern for prospective safety monitoring and safety assessment within this trial, e.g. the potential for AEs based on knowledge from other compounds in the same class. AESIs need to be reported to the sponsor’s Pharmacovigilance Department within the same timeframe that applies to SAEs, please see [Section 5.2.2.2](#).

The following are considered as AESIs:

- Hepatic injury

A hepatic injury is defined by the following alterations of hepatic laboratory parameters:

- an elevation of AST (aspartate transaminase) and/or ALT (alanine transaminase) ≥ 3 -fold ULN combined with an elevation of total bilirubin ≥ 2 -fold ULN measured in the same blood sample, or
- aminotransferase (ALT, and/or AST) elevations ≥ 10 fold ULN

These lab findings constitute a hepatic injury alert and the subjects showing these lab abnormalities need to be followed up according to the 'DILI checklist' provided in the ISF. In case of clinical symptoms of hepatic injury (icterus, unexplained encephalopathy, unexplained coagulopathy, right upper quadrant abdominal pain, etc.) without lab results (ALT, AST, total bilirubin) available, the Investigator should make sure that these parameters are analysed, if necessary in an unscheduled blood test. Should the results meet the criteria of hepatic injury alert, the procedures described in the DILI checklist should be followed.

Intensity (severity) of AEs

The intensity (severity) of the AE should be judged based on the following:

- Mild: Awareness of sign(s) or symptom(s) that is/are easily tolerated
- Moderate: Sufficient discomfort to cause interference with usual activity
- Severe: Incapacitating or causing inability to work or to perform usual activities

Causal relationship of AEs

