7.8.2 Laboratory data

The analyses of laboratory data will be descriptive in nature and will be based on BI standard "Display and Analysis of Laboratory Data" ([10](#)).

Analyses will be based on normalised values, which means transforming to a standard unit and a standard reference range.

Descriptive statistics of laboratory values over time and for the difference from baseline (see [Section 6.7](#)) will be provided. Frequency tables of changes between baseline and last value on treatment with respect to the reference range will be presented.

Unscheduled measurements of laboratory data will be assumed to be repeat measurements of the most recent scheduled measurement (e.g. for follow-up or confirmation of a particular value). Therefore, unscheduled measurements will be assigned to the planned time point of the previous scheduled measurement. Descriptive statistics will be calculated by planned time point based on the worst value of the subject at that planned time point (or assigned to that planned time point).

Possibly clinically significant abnormal laboratory values are only those identified either in the Investigator's comments on the eCRF or at the RPM/DBLM at the latest. It is the Investigator's responsibility to decide whether a lab value is clinically significant abnormal or not. Standard or project-specific rules for flagging clinically significant values will not be applied in this study.

Clinically relevant findings in laboratory data will be reported as AEs and will be analysed as part of AE analysis.

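### The SAP rule for unscheduled laboratory values, read per analyte, puts a post-dose liver test taken before Day 15 in the pre-dose row of the summary table

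*SAP*

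**What the plan says.** SAP 7.8.2 starts from an assumption: "Unscheduled measurements of laboratory data will be assumed to be repeat measurements of the most recent scheduled measurement". The assignment follows from it: "Therefore, unscheduled measurements will be assigned to the planned time point of the previous scheduled measurement". The summary rule is then: "Descriptive statistics will be calculated by planned time point based on the worst value of the subject at that planned time point", and values assigned to a time point count there as well. The same section tabulates differences from baseline, and a shift against the reference range from baseline to the last on-treatment value. SAP 6.7 defines baseline as the last non-missing value before dosing.

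In the protocol Flow Chart, the pre-dose safety laboratory on Day 1 carries footnote 3, under which "the procedure is to be performed and completed within 2 h prior to drug administration". The draws at 4, 48 and 168 h carry footnote 8: "Only measurement of haematocrit". The next full panel is at 336 h on Day 15, in the row labelled "Discharge from trial centre".

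For clinical symptoms of hepatic injury without liver results, protocol 5.2.2.1 asks the investigator to have AST, ALT and total bilirubin analysed, "if necessary in an unscheduled blood test".

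**The concern.** Treating an unscheduled value as a repeat is sensible when it confirms or corrects a recent sample. It does not fit a liver test prompted by new symptoms days after dosing, which is new post-dose information. The schedule leaves a long stretch with no liver panel, so the most recent scheduled liver measurement for such a test is the one taken before dosing. Because the worst value is then summarised, the post-dose result displaces the true pre-dose result in the by-time-point table.

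At stake is a table of laboratory values over time that shows an abnormality before the drug was given and nothing after it, in a trial where hepatic injury is the only adverse event of special interest. The pre-dose row would also disagree with the SAP's own baseline.

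**Working it through.** The plan gives no figure for this point. The check applies the stated rule to the stated schedule.

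**Inputs**
- Full safety laboratory, planned times (Flow Chart): -18 h, -2 h, 336 h and, for subjects who return, 821 h, plus end of trial.
- Haematocrit only (Flow Chart, footnote 8): 4, 48 and 168 h.
- Rule (SAP 7.8.2): an unscheduled value at time t goes to the latest scheduled time not after t.
- End of on-treatment phase (SAP Table 6.1:1): 11 × 24 h = 264 h after dosing.

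**Step 1: where an unscheduled liver test lands**

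| Test taken at (h) | Previous scheduled liver panel | Previous laboratory draw of any kind |
|---|---|---|
| 1, 3 | -2 h | -2 h |
| 5, 24, 47 | -2 h | 4 h |
| 49, 100, 167 | -2 h | 48 h |
| 169, 240, 300, 335 | -2 h | 168 h |

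The gap between scheduled liver panels is 336 - (-2) = 338 h. Read per analyte, all post-dose time up to 336 h maps to pre-dose. Read by any draw, 4/336 = 1.2% of it does, and later tests land in rows where no liver test is planned.

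**Step 2: effect on the summary (invented values, per-analyte reading)**

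Take six subjects, each with pre-dose ALT 25 U/L, and one unscheduled Day 5 value of 300 U/L. Worst is taken to mean highest.
- Pre-dose mean as intended: 25 U/L.
- Pre-dose mean under the rule: (5 × 25 + 300)/6 = 425/6 = 70.8 U/L.
- Baseline under SAP 6.7: still 25 U/L in every subject.
- Mean difference from baseline, if computed for the pre-dose row: (300 - 25)/6 = 45.8 U/L, where it should be zero.
- Post-dose rows before 336 h: no entry for the 300 U/L.

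In general, one value x above a common baseline b moves the pre-dose mean by (x - b)/6.

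**Step 3: the shift table**

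No full panel is scheduled from 0 to 264 h, so an unscheduled value is the only liver result that can fall in the on-treatment phase. Two passages decide whether it does:
- Protocol 7.3.3 assigns measurements to phases by planned time. A value given the -2 h planned time would go to screening and out of the shift table.
- SAP Table 6.1:1 sets the phase boundaries by date and time of dosing. A Day 5 value would be on treatment and would enter the shift table.

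The SAP does not say which governs a reassigned unscheduled value.

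**Step 4: vital signs**

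SAP 7.8.3 uses the same assignment but summarises the last value, not the worst. Vital signs are scheduled at -2, 4, 12 and 24 h, so only an unscheduled reading from 0 to 4 h can move to pre-dose.

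**The case against.** The strongest reply is that little of clinical importance depends on this table. Clinically relevant laboratory findings are reported and analysed as adverse events. Adverse events are assigned by recorded onset, so a Day 5 event is treatment-emergent wherever its laboratory value is tabulated. Hepatic injury is reported on the same timeline as serious events and has its own table. Individual values are listed and out-of-range values highlighted. A non-zero pre-dose difference from baseline would itself look odd to a careful reader. The example is invented, and protocol 1.2.4 reports no adverse events of special interest and, in general, no clinically relevant laboratory findings in earlier trials.

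Most of this stands, and it rules out several stronger readings that a reader might infer:
- That the safety signal is lost. It is not, for the reasons just given.
- That change over time is biased towards no drug effect. SAP 6.7 keeps baseline at the true pre-dose value, so the Day 15 change from baseline is untouched, and by actual time the value would enter the shift table.
- That every analyte except haematocrit maps to the Day 1 sample. Table 5.2.3: 1 limits thyroid hormones, uric acid, cholesterol, triglycerides and urinalysis to screening and end of trial, so these map to screening.
- That the whole 14-day stay is exposed on any reading. That needs the per-analyte reading, which the repeat-measurement rationale favours but the SAP does not state. The sponsor's laboratory display standard, cited in the SAP, may settle it but is not available here.
- That vital signs are equally exposed. Step 4 shows they are not.

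The safeguards are still only partial. Adverse event reporting of a laboratory value rests on investigator judgement, and SAP 7.8.2 declines standard flagging rules. A transaminase rise below 10-fold ULN without the bilirubin criterion is not an event of special interest. The documents give no ULN; if it were 40 to 50 U/L, 300 U/L would be 300/50 = 6 to 300/40 = 7.5 times ULN.

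**Conclusion.** The rule as written gives a wrong summary in a situation the protocol itself anticipates. Under the per-analyte reading, an unscheduled liver test at any time between dosing and 336 h is summarised as pre-dose. Under the any-draw reading this happens only up to 4 h; a later value does appear after dosing, but at a nominal time with no scheduled liver test.

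The size depends on an event that may not occur. If it does, one value is enough to distort a six-subject row, as in the illustrative shift from 25 to 70.8 U/L. The damage is confined to the by-time-point statistics and, if planned time governs phases, to the shift table. This is a correction worth making to the summary tables. It is not evidence that the plan would miss a liver signal.

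**What to change.** In SAP 7.8.2, state that a value taken after drug administration is never assigned to a pre-dose time point. Show such values in a separate row for unscheduled post-dose measurements. Assign them to the analysis phase by actual date and time, so that a value before 264 h counts in the existing shift table from baseline to last on-treatment value. No new shift analysis is needed.

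State whether the previous scheduled measurement is determined per analyte. Apply the same bar to vital signs in SAP 7.8.3, where it matters only from 0 to 4 h. Reconcile protocol 7.3.3 (planned time) with SAP Table 6.1:1 (date and time of dosing) for measurements.

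The cost is a few sentences of SAP text, a small programming condition and one extra table row that will usually hold no or one subject. No additional data are needed.

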7.8.3 Vital signs

The analysis of vital signs will be descriptive in nature. Descriptive statistics of vital signs over time and for the difference from baseline (see [Section 6.7](#)) will be provided.

Unscheduled measurements of vital signs will be assigned to planned time points in the same way as described above for laboratory data. However, for vital signs, descriptive statistics will be calculated by planned time point based on the last value of the subject at that planned time point (or assigned to that planned time point).

Clinically relevant findings in vital signs data will be reported as baseline conditions (at screening) or as AEs (during the trial) if judged clinically relevant by the investigator, and will be analysed as such.

7.8.4 ECG

Abnormal findings in 12-lead ECG will be reported as baseline conditions (at screening) or as AEs (during the trial) if judged clinically relevant by the investigator, and will be analysed as such. No separate listing or analysis of ECG data will be prepared.

7.8.5 Others

Physical examination findings will be reported as relevant medical history/baseline condition (i.e., a condition already existent before intake of first study drug) or as AE and will be summarised as such. No separate listing or analysis of physical examination findings will be prepared.

10. HISTORY TABLE

Table 10: 1 History table

Version	Date (DD-MMM-YY)	Author	Sections changed	Brief description of change
Final	15-JAN-2019		None	This is the final TSAP without any modification
